## 5.0 STUDY PROCEDURES

	Screening (-28 days)	On Treatment 		Off Treatment	
Time Period	Baseline	Cycle 1+ (+/- 3days)	After Every 3 cycles	End of Treatment	Follow-up 
Assessment or Activity					
Informed Consent	X				
Medical history (H)	X			X	
Concomitant Medications 	X	X		X	X 
Vitals, Physical exam  (PE) 	X	X		X	
ECOG status	X	X		X	
Toxicity assessment 		X		X	X 
Tumor Measurements 	X		X 	X	
Biopsy/archival tissue 	X				
CBC with diff 	X	X		X	
Chemistry panel 	X	X 		X	
PT/PTT/INR 	X				
Thyroid function tests 	X		X 		
Pregnancy test 	X				
Pembrolizumab 		X			
Capecitabine 		X			
Survival status					X

 Every physical exam will be a full physical exam and is standard of care. It will include vital signs (pulse, temperature, and blood pressure) and height (baseline only) and weight.

 CT c/a/p AND bone scan. In place of bone scan, a PET/CT may be used. If CT is contraindicated, MRI may be used. Any additional imaging such as MRI can be completed at the physician's discretion. The same modality should be used throughout the study. The baseline procedure is to be performed within 28 days prior to registration. Subsequently, it will be done prior to the start of the next treatment cycle e.g 4, 7, 10 etc. For patients who are unable to obtain scans at the designated time points, a window of 7-10 days is allowed. This exception is not applicable to the screening period. Bone scans are to be repeated at each time point ONLY if the patient has bone metastasis or if it is clinically indicated. If the original bone scan during screening is negative, then bone scans are not required in subsequent visits.

 A baseline tissue biopsy of a metastatic site will be obtained for PD-L1 immunohistochemical (IHC) assessment, from all patients. An archived specimen may be used (metastatic tissue only) if collected no more than 2 months prior to registration. Otherwise fresh biopsy of metastatic lesion is mandatory at baseline and should be performed no more than 2 months prior to registration. The requirement for biopsy (fresh) may be omitted per treating physician's discretion, if the biopsy would cause undue morbidity to the patient and if enough tissue from a prior metastatic lesion (archival biopsy) is not available.

PD-L1 IHC assay from QualTek will be used for the study.  
Please refer to section 9.1 and laboratory manual for more details

 Hematology will include white blood cells (WBC) with differential, platelet count, hematocrit, and hemoglobin. To be performed within 14 days before Day1

 Serum Chemistry will include calcium, chloride, creatinine, sodium, potassium, blood urea nitrogen, bicarbonate, glucose, total bilirubin, aspartate aminotransferase (AST), alanine aminotransferase (ALT), alkaline phosphatase (ALP), albumin, and total protein. To be performed within 14 days prior to registration. Patients with liver metastasis will have additional liver function testing done on C1D7 and C1D14, which can be done locally and sent to NU for review.

 This is to be done if the patient is required to have a biopsy (in order to test for bleeding parameters before biopsy). It is to be performed and resulted before the biopsy. (Also refer to footnote 14)

 Serum or urine test for females of child-bearing potential.

 Pembrolizumab will be administered IV at the assigned dose, at Day 1 of every cycle (1cycle =21 days)

 Capecitabine will be self-administered orally by patients at a fixed dose daily on Days 1-14 twice daily, of each cycle.

 A cycle is defined as 21 days (+/- 3 days).

 Patients will be assessed every 3 months up to 2 year after discontinuation of the study drugs for PFS with visits and/or phone calls.

 concomitant medications to be recorded during screening, at the beginning of each cycle and for 30 days after end of treatment

Thyroid function will be evaluated at baseline (performed within 14 days of Day1) and prior to the start of the next treatment cycle e.g. 4, 7, 10 etc. The tests included are TSH, freeT3, and freeT4.

Toxicity assessment to be done at the beginning of each cycle, at the end of treatment visit and for 30 days after end of treatment.

## 6.0 ENDPOINT ASSESSMENT

### 6.1 Disease Definitions

Patients with non-measurable and measurable disease are eligible for this study. Response to treatment will be assessed using RECIST1.1 guidelines (Appendix 3). Response and progression will be assessed in this study via physical exam and imaging. Lesions are defined as either measurable or non-measurable using the criteria provided below.

#### 6.1.1 Measureable Disease

Measurable disease per RECIST 1.1 is defined as the presence of at least one measurable lesion. Measurable lesions are defined as those that can be accurately measured in at least one dimension (longest diameter to be recorded) as  $\geq 20$  mm by chest x-ray, as  $\geq 10$  mm with CT scan, or  $\geq 10$  mm with calipers by clinical exam. For irRC, measurable lesions are defined as as those that can be accurately measured in at least two dimensions as 10x10mm with CT scan. All tumor measurements must be recorded in millimeters.

#### 6.1.2 Non-Measurable Disease

For both RECIST 1.1 and irRC, all other lesions (or sites of disease), including small lesions (longest diameter  $< 10$  mm or pathological lymph nodes with  $\geq 10$  to  $< 15$  mm short axis), are considered non-measurable disease. Bone lesions, leptomeningeal disease, ascites, pleural/pericardial effusions, lymphangitis cutis/pulmonitis, inflammatory breast disease, and abdominal masses (not followed by CT or MRI), are considered as non-measurable.

Evaluation of Overall Timepoint Response for Patients without Measurable disease at baseline

Non-target	New	Overall Response
CR	No	CR
Non-CR/Non-PD	No	Non-CR/Non-PD
Not all evaluated	No	NE
Unequivocal Progression	Yes or No	PD
Any	Yes	PD

CR=Complete Response, PD=Progressive disease, NE=Inevaluable

#### 6.1.3 Target Lesions

When more than one measurable lesion is present at baseline all lesions up to a maximum of five lesions total (and a maximum of two lesions per organ) representative of all involved organs should be identified as target lesions and

will be recorded and measured at baseline (this means in instances where patients have only one or two organ sites involved a maximum of two and four lesions respectively will be recorded). Target lesions should be selected on the basis of their size (lesions with the longest diameter), be representative of all involved organs, but in addition should be those that lend themselves to reproducible repeated measurements. It may be the case that, on occasion, the largest lesion does not lend itself to reproducible measurement in which circumstance the next largest lesion which can be measured reproducibly should be selected.

Target lesions should be selected on the basis of their size (lesions with the longest diameter) and their suitability for accurate repeated measurements (either by imaging techniques or clinically). A sum of the longest diameter (LD) for all target lesions will be calculated at baseline and used as the reference by which to characterize the objective tumor response.

#### **6.1.4 Non-Target Lesions**

All other lesions (or sites of disease) should be identified as non-target lesions and should also be recorded at baseline. Non-target lesions include measurable lesions that exceed the maximum numbers per organ or total of all involved organs as well as non-measurable lesions. Measurements of these lesions are not required.

### **6.2 Guidelines for Evaluation of Measureable Disease**

All measurements should be taken and recorded in metric notation using a ruler or calipers. All baseline evaluations should be performed within the timeframe noted in section 5.0. The same method of assessment and the same technique should be used to characterize each identified and reported lesion at baseline and during follow-up. Imaging-based evaluation is preferred to evaluation by clinical examination when both methods have been used to assess the antitumor effect of a treatment.

#### **6.2.1 Clinical lesions**

Clinical lesions will only be considered measurable when they are superficial and P10 mm diameter as assessed using calipers (e.g. skin nodules). For the case of skin lesions, documentation by color photography including a ruler to estimate the size of the lesion is suggested. As noted above, when lesions can be evaluated by both clinical exam and imaging, imaging evaluation should be undertaken since it is more objective and may also be reviewed at the end of the study.

### **6.3 Endpoints**

#### **6.3.1 Primary Endpoint(s):**

To evaluate the median progression-free survival (median PFS) for participants receiving pembrolizumab with capecitabine for the treatment of locally advanced or metastatic TNBC and hormone-refractory MBC. This will be assessed by using RECIST 1.1 criteria.

**Complete Response (CR):** Disappearance of all target lesions. Any pathological lymph nodes (whether target or non-target) must have reduction in short axis to <10 mm.

**Partial Response (PR):** At least a 30% decrease in the sum of diameters of target lesions, taking as reference the baseline sum diameters.

**Progressive Disease (PD):** At least a 20% increase in the sum of diameters of target lesions, taking as reference the smallest sum on study (this includes the baseline sum if that is the smallest on study). In addition to the relative increase of 20%, the sum must also demonstrate an absolute increase of at least 5 mm. (Note: the appearance of one or more new lesions is also considered progression).

**Stable Disease (SD):** Neither sufficient shrinkage to qualify for PR nor sufficient increase to qualify for PD, taking as reference the smallest sum diameters while on study.

Please note patients with PD may stay on study with PD if they meet the criteria in section 4.2.3.

*Any patient who has completed **at least 3 cycles** of pembrolizumab and capecitabine will be evaluable for this endpoint.*

*Note: the first set of scans is required to establish that the patient is evaluable for this endpoint.*

### 6.3.2 Secondary Endpoints:

To describe the objective response rate (ORR) for participants receiving pembrolizumab with capecitabine for the treatment of locally advanced or metastatic TNBC and hormone-refractory MBC.

This will be assessed by using RECIST 1.1 criteria (appendix 3).

*Any patient who has completed **at least 3 cycles** of this combination therapy are evaluable for this endpoint. Note: the first set of scans is required to establish that the patient is evaluable for this endpoint.*

To describe the safety and tolerability of the combination of pembrolizumab and capecitabine for the treatment of locally advanced or metastatic TNBC and hormone-refractory MBC. All adverse events will be assessed by NCT CTCAE 4.03 criteria.

*Any patient who has completed **at least one dose** of either pembrolizumab or capecitabine will be evaluable for this endpoint.*

*(NOTE: If a patient discontinues treatment due to early progression prior to completing 3 cycles of therapy, the patient will be evaluable for toxicity but not for efficacy endpoints; in this case an additional patient may be added).*

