#### 4.8 Patient Replacement

If a patient is withdrawn from the study prior to completing 21 days of therapy, for reasons other than adverse event or progression of disease, an additional patient may be added. If a patient discontinues treatment due to early progression prior to completing 3 cycles of therapy, the patient will be evaluable for toxicity but not for efficacy endpoints; in this case an additional patient may be added. (*Note: any patient receiving 1 dose of pembrolizumab is evaluable for toxicity but not for primary objective of PFS*).

Patients missing 14 or more doses of capecitabine due to toxicity will not be replaced.

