**QualTek Molecular Laboratories**  
**MISP Receiving**  
**[name]**  
**[name]**  
**[contact]**  
**Email: [[contact]](mailto:[contact])**

## 10.0 STATISTICAL CONSIDERATIONS

For PFS, assumptions are that the addition of pembrolizumab will increase PFS to 5  
months compared to historical control of 3 months. Assuming exponential survival, with  
27 evaluable patients, there is 80% power to detect this difference using a one-  
tailed z test at  $p < 0.05$ .

Recruitment of 30 participants to accrue 27 evaluable will last approximately 30 months  
(2.5 years) and participants will be followed for a maximum of 2 years from enrollment of  
the last patient. The primary outcomes chosen is PFS based on mechanism of action..

PFS will be analyzed using a Kaplan-Meier curve. A confidence interval for the median  
PFS will be calculated (Brookmeyer, R. and Crowley, J. (1982), "A Confidence Interval for  
the Median Survival Time," *Biometrics*, 38, 29-41.), and if the confidence interval is  
totally above 3 months, then it may be concluded that the PFS exceeds 3 months.

Objective response rate will be summarized using a proportion and an exact 95% binomial confidence interval. Anti-tumor activity will be reported as a percentage change in the sum of the dimensions of all measurable lesions as defined by RECIST 1.1 criteria. The baseline imaging before treatment will be compared to each subsequent imaging assessment. The maximum anti-tumor activity will be reported using the assessment with the smallest sum of dimensions (maximum response).

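### The ORR denominator drops patients who stop early for progression but keeps patients without measurable disease, who cannot have a partial response

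*Combined protocol and SAP*

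**What the plan says.** Three sets of statements together fix the ORR denominator.

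- **Who is counted.** Section 6.3.2 states that patients with at least 3 completed cycles "of this combination therapy are evaluable for this endpoint", and that the first scans are needed to establish this. For a patient who stops for early progression before completing 3 cycles, Section 4.8 says "the patient will be evaluable for toxicity but not for efficacy endpoints; in this case an additional patient may be added". Section 6.3.2 repeats that rule.
- **Who may enrol.** Section 6.1 says "Patients with non-measurable and measurable disease are eligible for this study", and no criterion in Section 3.1 or 3.2 requires measurable disease. Section 6.1.2 has a table headed "Evaluation of Overall Timepoint Response for Patients without Measurable disease at baseline". It offers CR, Non-CR/Non-PD, NE and PD, and no PR. Section 6.3.1 defines PR on the sum of diameters of target lesions.
- **How it is analysed.** Section 10 says "Objective response rate will be summarized using a proportion and an exact 95% binomial confidence interval". It names no analysis set, null rate or target for ORR.

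Section 10 also promises a "percentage change in the sum of the dimensions of all measurable lesions as defined by RECIST 1.1 criteria". Section 6.1.3 takes as targets "all lesions up to a maximum of five lesions total (and a maximum of two lesions per organ". For measurable lesions beyond those caps, which become non-target, Section 6.1.4 says "Measurements of these lesions are not required".

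**The concern.** The objective in Section 2.2 is ORR for participants receiving the combination. The set in Section 6.3.2 is a different one, selected partly on outcome: a patient whose disease progresses quickly enough to stop treatment before the end of cycle 3 is a non-responder, yet is removed and may be replaced by someone else. The 3-cycle wording also removes patients who stop early for toxicity, withdrawal or death. Taking non-responders out of the denominator biases ORR upward.

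Patients without measurable disease work in the other direction. They can reach ORR only through a CR, so the same proportion mixes patients who can and cannot have a PR.

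The reported ORR would therefore depend on how many early failures were dropped and how many non-measurable patients were enrolled. The plan does not require the report to show either count. No test depends on ORR, but readers will compare it with the single-agent rates in Section 1.2, and Section 6.3.3 plans to correlate response with PD-L1 expression.

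A smaller point is that the percentage-change statistic, read literally, may not be computable for patients with more measurable lesions than the target caps allow.

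**Working it through.** The documents give no sample size, power or target for ORR, so there is no stated figure to reproduce. The check measures how far each rule moves the estimate.

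**Inputs from the protocol**
- 30 accrued to obtain 27 evaluable (Study Summary; Section 10).
- Exponential PFS with median 3 months (historical) or 5 months (target) (Section 10).
- First on-treatment scan after 3 cycles, at 9 weeks (Sections 5.0 and 6.3.3).
- Illustrative true ORR of 20%, the single-agent capecitabine rate quoted in Section 1.2.2.

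**Assumed, because the documents give no figure**
- Share without measurable disease, q = 10%, 25% or 40%.
- CR rate among them, 0% or 5%.

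**1. Early failures removed, at the plan's own allowance.** Take 6 responders among 30 treated, all of them among the 27 evaluable. Exact (Clopper-Pearson) 95% intervals:
- 6/30 = 20.0% (7.7% to 38.6%)
- 6/27 = 22.2% (8.6% to 42.3%)

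**2. Upper bound on exclusion.** Nine weeks = 63/30.4375 = 2.07 months. The share progressing or dying by then is 1 − 2^(−2.07/median):
- median 5 months: 24.9%
- median 3 months: 38.0%

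These are upper bounds for exclusion through progression or death, because a patient whose progression is first seen on the cycle-3 scan has completed 3 cycles and stays in.

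**3. Inflation and coverage.** If a share e, all non-responders, is removed, the reported rate tends to 0.20/(1 − e). Coverage is the probability that the exact 95% interval at n = 27 contains the true 20%, with responders distributed as Bin(27, 0.20/(1 − e)). That interval contains 20% when there are 2 to 10 responders.

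| e | Expected reported ORR | Coverage of 20% |
|---|---|---|
| 0 | 20.0% | 97.0% |
| 10% | 22.2% | 96.6% |
| 25% | 26.7% | 91.8% |
| 38% | 32.3% | 77.2% |

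Reaching 27 evaluable at e = 25% or 38% would take 27/0.75 = 36 or 27/0.62 ≈ 44 treated patients, more than the 30 planned. With accrual held at 30, about 22 or 19 remain evaluable, and coverage is similar: 89.4% and 75.4%.

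**4. Dilution by non-measurable disease.** With 20% ORR among measurable patients and CR rate c in the others, the pooled rate is 0.20(1 − q) + c·q.

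| q | c = 0 | c = 5% |
|---|---|---|
| 10% | 18.0% | 18.5% |
| 25% | 15.0% | 16.3% |
| 40% | 12.0% | 14.0% |

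**5. Both together**, with c = 0 and exclusion independent of measurability: 0.20(1 − q)/(1 − e).
- e = 10%, q = 40%: 0.12/0.90 = 13.3%
- e = 25%, q = 25%: 0.15/0.75 = 20.0%
- e = 38%, q = 10%: 0.18/0.62 = 29.0%

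**6. An illustration from the background.** For the phase Ib study of pembrolizumab in PD-L1-positive disease, Section 1.2.1 reports 32 treated and rates of 3.7%, 14.8%, 25.9% and 18.5%. These fit 1, 4, 7 and 5 of 27. On all 32 treated, 5/32 = 15.6%. The protocol does not say why 27 was used.

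**The case against.** The strongest objection is that little depends on this. ORR is to be described, with no null, threshold or decision rule. At the planned 27 of 30 the estimate moves by 2.2 points, against an interval more than 30 points wide, and coverage stays at 96.6%. The larger figures rest on exclusion shares that are upper bounds and on non-measurable shares with no source in the documents. Section 4.2.3 also lets patients with suspected pseudoprogression stay on treatment, which further limits early exclusion. The 3-cycle set is pre-specified and openly stated. Reasons for discontinuation go on the eCRF (Section 4.7), so the counts will exist. The background study says nothing about a defect in this plan. The percentage-change wording can be read with Section 6.1.3, which makes the target-lesion sum the reference for response.

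Much of this stands as a limit on size. The 10% case is the one tied to the plan's own numbers, the rest is a range, and the background figures only illustrate that a denominator matters. The percentage-change point is loose wording that one sentence settles.

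The definition itself is not rescued. Pre-specifying a rule that removes failures because they failed does not make the result an estimate for treated patients. Two opposing biases of unknown size cannot be assumed to cancel. That the counts will be recorded does not make the plan use them.

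**Conclusion.** The concern holds. Followed as written, the plan yields an ORR that does not match its stated objective: patients who stop early for progression leave the denominator, patients who cannot have a PR remain in it, and Section 10 supplies no alternative set.

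The size is modest at the plan's own allowance (20.0% becomes 22.2%). It could be material if early stopping is more frequent or non-measurable disease is common: a true 20% could be reported as anything from 13% to 29%. That range assumes no CR in non-measurable patients, exclusion independent of measurability, assumed non-measurable shares of 10% to 40%, and exclusions of 10% to 38%, of which 25% and 38% are upper bounds. The net direction cannot be determined from the documents.

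No error rate or trial decision is affected, so this should be corrected but does not threaten the primary analysis. The arithmetic reproduces, and confidence in the reading is high.

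**What to change.** Amend Section 6.3.2, the efficacy-evaluability note in Section 4.8 as it applies to ORR, and Section 10. Suggested text:

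> ORR is the proportion with CR or PR among all treated patients with measurable disease at baseline, with an exact 95% confidence interval. Early progression, death, or absence of any post-baseline assessment counts as non-response; any recorded end-of-treatment assessment is used. Patients without measurable disease are described separately (CR, Non-CR/Non-PD, PD, NE). ORR in patients completing at least 3 cycles is a sensitivity analysis. Percentage change is calculated on the sum of target-lesion diameters.

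The report should give the number treated, the number with measurable disease, and the number not completing 3 cycles, with reasons.

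**Cost.** Wording only, because Section 5.0 already schedules baseline and end-of-treatment tumor measurements. The denominator may grow or shrink: early failures come back in, and of 30 treated about 27, 22 or 18 would have measurable disease if 10%, 25% or 40% do not. The ORR may look less favourable and its interval may be wider.

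This change covers ORR only. Section 6.3.1 applies the same 3-cycle rule to PFS, so the two efficacy populations would differ unless that rule is also addressed.

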### 6.3.3 Exploratory Endpoint: PD-L1 assessment

A baseline tissue biopsy of a metastatic site will be obtained for PD-L1 immunohistochemical (IHC) assessment, from all patients. An archived specimen may be used (metastatic tissue only) if collected no more than 2 months prior to registration. Otherwise fresh biopsy of metastatic lesion is mandatory at baseline and should be performed no more than 2 months prior to registration.

*Note: The requirement for biopsy (fresh) may be omitted per treating physician's discretion, if the biopsy would cause undue morbidity to the patient and if enough tissue from a prior metastatic lesion (archival biopsy) is not available.*

*Note: PD-L1 IHC assay from QualTek will be used for the study. Please refer to section 9.1 and laboratory manual for more details*

QualTek developed and validated a PD-L1 IHC assay using Merck's proprietary

IRB #: STU00203215 Approved by NU IRB for use on or after 9/16/2019 through 9/15/2020.  
 22C3 antibody, and this will be used for the study. The study site's pathology core will be used to store, process, and ship samples to QualTek. The presence of PD-L1 expression will be correlated with response (PFS, RR) and other clinical-pathologic factors in an attempt to define a subset of patients that may benefit from pembrolizumab.

